## 6.2. Subject Exclusion Criteria

Subjects who meet any of the following criteria will be excluded from the study:

- Urgent need of treatment to prevent acute neurologic deterioration, including urgent neurosurgery or radiotherapy
- Symptoms of uncontrolled intracranial pressure
- Symptomatic or untreated spinal cord compression
- Prior treatment with any chemotherapeutic or investigational agent
- Prior treatment with any BRAF and/or MEK inhibitor for metastatic disease
- Prior treatment with > 1 line of immunotherapy for metastatic disease
- Serious cardiac condition within the last 6 months, such as uncontrolled arrhythmia, myocardial infarction, unstable angina or heart disease defined by the New York Heart Association (NYHA) Class III or Class IV (APPENDIX C)
- QT interval corrected for rate (QTc) > 480 msec on the ECG obtained at Screening using Fridericia method for QTc calculation
- Active infection with human immunodeficiency virus (HIV), hepatitis B virus (HBV) or hepatitis C virus (HCV) requiring systemic antiviral treatment within the last week prior to study treatment

Confidential 40
December 31, 2019 Protocol Amendment 4

• Other active infection requiring IV antibiotic usage within the last week prior to study treatment

- Any other medical intervention or other condition which, in the opinion of the Principal Investigator, could compromise adherence to study requirements or confound the interpretation of study results
- Pregnant or breast-feeding

### 6.3. Discontinuation of Subjects

#### 6.3.1. Procedures for Withdrawal

Any subject may be removed from study for the following reasons:

- Subject withdrawal of the informed consent
- Subject noncompliance
- An increasing or unexpected pattern of unacceptable toxicity
- Disease progression or confirmed loss of clinical response
- Investigator judgment when the well-being and best interest of the subject is compromised

Subjects experiencing unacceptable toxicity should be removed from the study once complete resolution of toxicity has been documented. Individual subjects may be discontinued from the study by the investigator or sponsor at any time if either determines that it is not in the best interest of the subject to continue.

Any subject who becomes pregnant during the study must be discontinued from the study immediately but should be followed through delivery or termination of the pregnancy. Subjects should also notify the investigator if they become pregnant within 28 days following the last dose of study drug. Spirita Oncology also must be notified if a subject becomes pregnant on study.

If a subject is discontinued from the study before completing the specified duration of treatment, they should be encouraged to complete the end-of-study assessments and to agree to report any serious adverse events for 28 days following the last dose of study drug. The date the subject is withdrawn and the primary reason for discontinuation will be recorded on the case report form (CRF).

#### 6.3.2. Replacement of Study Subjects

Subjects who are screened but do not receive E6201 or dabrafenib in Combination Safety Run-in and Expansion Phases, and subjects treated in Cycle 1 who do not complete 4 of 6 doses (e.g., D1, 4, 8, 11, 15 and 18) of their prescribed E6201 study drug treatment, or do not complete 67% of their daily dabrafenib doses, or do not complete the C1D28 evaluation due to progression of disease, withdrawal of consent or non-drug-related adverse events, will be replaced. Subjects who meet one of the above criteria but also experience a DLT will not be replaced with respect to assessment of an MTD for the combination treatment regimen of E6201 plus dabrafenib.

Confidential 41
December 31, 2019 Protocol Amendment 4

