#### **Protocol Number: STX-101-02**

disease, observation of unacceptable adverse events, intercurrent illness or changes in the subject's condition that prevents further study participation.

Number of Subjects and Centers (planned): A total of 4 subjects were enrolled in the Monotherapy Safety Run-in Phase. A total of 6 - 12 subjects are anticipated in the Combination Safety Run-in Phase. A total of up to 18 subjects will be enrolled in the Expansion Phase for a total N = 28 - 34 for the study. Study centers include University of Arizona ([name] - Study Chair) and additional study centers as needed to ensure timely study accrual.

**Duration of Study:** Accrual is expected to be 24 months, with the last subject followed for up to 6 months. The total study duration is expected to be 30 months. The anticipated accrual rate is 1-2 subjects per month.

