Dose-limiting toxicity (DLT) is defined as any one of the following events:

- Grade 4 hematologic toxicity for > 1 day
- Grade 3 hematologic toxicity with complications (e.g., thrombocytopenia with bleeding)
- Failure of Grade 3 thrombocytopenia, absolute neutrophil count (ANC), hemoglobin to recover to Grade ≤ 1 within 4 weeks despite the use of platelet and red blood cell (RBC) transfusions and/or growth factors

Confidential 30
December 31, 2019 Protocol Amendment 4

• ≥ Grade 3 non-hematologic toxicity not due to disease progression (excluding Grade 3 nausea, vomiting or diarrhea that is adequately controlled with supportive care and resolves to ≤ Grade 2 within 48 hours, or Grade 3 electrolyte disturbances responsive to correction within 24 hours)

- ≥ Grade 3 liver function tests (LFTs) lasting > 72 hours
- Treatment interruption > 14 days due to toxicity
- Other important medical event

Subjects who require a dose reduction due to toxicity will be considered to have had a DLT.

If a DLT is experienced in  $\geq 2$  of 6 subjects in the Combination Safety Run-in Phase during Cycle 1, no further subjects will be enrolled at that dose level. Subjects who experience a DLT may continue treatment at the next lower dose level until disease progression or unacceptable toxicity. The MTD is defined as the doses of E6201 plus dabrafenib at which  $\leq 1$  of 6 subjects experiences a DLT.

E6201 dose reductions for suspected E6201-related toxicity will be 240 mg/m^2 twice weekly (Dose Level -1) and 160 mg/m^2 twice weekly (Dose Level -2), administered over the same schedule as above, Days 1, 4, 8, 11, 15 and 18, repeated every 28 days.

Dabrafenib dose reductions for suspected dabrafenib-related toxicity will be 100 mg (Dose Level -1), 75 mg (Dose Level -2) and 50 mg (Dose Level -3) orally twice daily, according to the U.S. Product Label.

A total of 6 subjects will be treated at the combined MTD doses for both drugs established in the Combination Safety Run-in Phase before beginning the Expansion Phase.

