Expansion Phase: Following screening, an additional cohort of up to N=18 subjects will be treated at the E6201 plus dabrafenib combined MTD. Subjects treated at the MTD in the Combination Safety Run-in Phase will count towards accrual in the Expansion Phase. E6201 will be administered by IV infusion over a 2-hour period at the MTD and schedule determined in the Combination Safety Run-in phase, repeated every 28 days (=1 cycle), and dabrafenib will be administered orally twice daily at the MTD determined in the Combined Safety Run-in phase. Both regimens will be subject to dose reductions for toxicity, as described. Subjects who demonstrate clinical benefit (objective response or stable disease) will be allowed to continue therapy with E6201 plus dabrafenib until progression of disease, observation of unacceptable adverse events, intercurrent illness or changes in the subject's condition that prevents further study participation.

During the study, a Safety Review Committee (SRC), consisting of the actively recruiting investigators, the Sponsor Medical Monitor and study staff will review data from the Monotherapy and Combination Safety Run-in Phases before beginning the Expansion Phase, and will review data from the Expansion Phase on an ongoing basis.

The statistical objective is the evaluation of the intracranial disease objective response (OR) rate, defined as complete response (CR) or partial response (PR), on treatment with E6201 plus dabrafenib. The sample size is based on a one-arm binomial design  $H_0 \le 0.05$  ( $\le 5\%$  response rate for historical control group) versus  $H_1 > 0.05$  (> 5% response rate for experimental group). An objective response (OR) rate of 25% or greater is deemed clinically important. A total of 3 or more

Confidential 31
December 31, 2019 Protocol Amendment 4

responses in a sample size of 18 subjects indicates the true OR rate is  $\geq$  25%, with power of = 80%, alpha = 0.05, and provides evidence of clinical utility to move forward.

CNS disease response will be assessed according to 2 methodologies: Response Evaluation Criteria in Solid Tumors (RECIST v. 1.1). and Response Assessment in Neuro-Oncology – Brain Metastases (RANO-BM). Clinical benefit is defined as best response of CR), (PR) or stable disease (SD).

Non-CNS systemic disease will be assessed according to RECIST v. 1.1.

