# **5.2.** Number of Subjects and Centers

A total of 4 subjects were enrolled in the Monotherapy Safety Run-in Phase. A total of 6-12 subjects are anticipated in the Combination Safety Run-in Phase. A total of up to 18 subjects will be enrolled in the Expansion Phase for a total of N=28-34 for the study. Study centers include University of Arizona ([name]), and additional study centers as needed to ensure timely accrual to the study.

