#### 11. STATISTICAL METHODOLOGY

#### 11.1. **Determination of Sample Size**

The statistical objective is the evaluation of the intracranial disease OR rate, defined as CR or PR, on treatment with E6201 plus dabrafenib. The sample size is based on a one-arm binomial design  $H_0 \le 0.05$  ( $\le 5\%$  response rate for historical control group) versus  $H_1 > 0.05$  (> 5% response rate for experimental group). An objective response rate (OR) of 25% or greater is deemed clinically important. A total of 3 or more responses in a sample size of 18 subjects indicates the true OR rate is  $\geq 25\%$ , with power = 80%, alpha = 0.05, and provides evidence of clinical utility to move forward.

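### The n behind the go rule of 3 or more responses in 18 is not settled: the plan supports 18 or 24 subjects at the MTD, and no analysis set is named for the primary rate

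*Combined protocol and SAP*

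**What the plan says.** **The rule.** Section 11.1, repeated in the Synopsis and Section 5.1, tests a null response rate of at most 5% and treats 25% or more as clinically important. It takes "A total of 3 or more responses in a sample size of 18 subjects" as evidence to proceed, with stated power of 80% and alpha of 0.05.

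**Who the 18 are.** Section 5.1 says that "an additional cohort of up to N=18 subjects will be treated at the E6201 plus dabrafenib combined MTD". It then says "Subjects treated at the MTD in the Combination Safety Run-in Phase will count towards accrual in the Expansion Phase". Their number is given just before: "A total of 6 subjects will be treated at the combined MTD doses for both drugs established in the Combination Safety Run-in Phase". The Synopsis repeats all three statements.

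**The totals.** Four subjects entered the monotherapy run-in. The Synopsis adds "A total of 6 - 12 subjects are anticipated in the Combination Safety Run-in Phase", and Section 5.2 concludes "A total of up to 18 subjects will be enrolled in the Expansion Phase for a total of N=28-34 for the study".

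**The analysis set.** Section 11.2 defines a full analysis set (FAS: anyone given any part of a dose of either drug) and a per-protocol set (PPS: FAS subjects with a valid baseline and at least one post-treatment assessment of the measure). Section 11.3.1.1 assigns safety to the FAS. Sections 10.4.1.1 and 11.3.2.1 assign no set to the primary intracranial response rate. Section 11.2 says only that efficacy is analysed separately for the monotherapy and combination phases; nothing limits the primary endpoint to the MTD level.

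**Replacement.** Section 6.3.2 opens with "Subjects who are screened but do not receive E6201 or dabrafenib in Combination Safety Run-in and Expansion Phases". It goes on to dosed Cycle 1 subjects who miss an E6201 or dabrafenib dose threshold, or who "do not complete the C1D28 evaluation due to progression of disease, withdrawal of consent or non-drug-related adverse events, will be replaced". MTD assessment appears only in the exception for subjects who had a DLT.

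**The concern.** The decision rule is written for one sample size. Percentages and 95% confidence intervals can be calculated at any n, but a cut-off of 3 means something different in 18 subjects than in 24. The plan leaves three things open: whether the 6 run-in subjects at the MTD are inside or outside the 18; whether subjects treated at other combination dose levels belong in the primary rate; and whether the denominator is everyone dosed or only those with a follow-up assessment.

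Replacement adds a smaller uncertainty. Section 6.3.2 does not say whether a dosed subject who is replaced stays in the response denominator. It reaches the primary sample even if it is read as a run-in rule, because Section 5.1 carries run-in subjects at the MTD into the Expansion count.

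The study is open-label. Unless n, the set and the cut-off are fixed in writing, they could be chosen once the responses are known.

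**Working it through.** **Inputs.** Null rate 5%, target rate 25%, n=18 and cut-off 3 (Section 11.1); 4 monotherapy subjects, 6-12 combination run-in subjects, up to 18 Expansion subjects and totals of 28-34 (Section 5.2); 6 run-in subjects at the MTD (Section 5.1). Sidedness is not stated in words; the hypotheses are directional, so alpha is read as one-sided. The documents give no replacement rate, so replacement counts are assumptions.

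**Step 1: the plan's own figure.** With X binomial(n, p), the chance of a go signal is P(X >= c) = 1 - sum over k<c of C(n,k) p^k (1-p)^(n-k).
- n=18, c=3, p=0.05: 1 - (0.3972 + 0.3763 + 0.1683) = 0.058.
- n=18, c=3, p=0.25: 1 - (0.0056 + 0.0338 + 0.0958) = 0.865.

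The stated alpha of 0.05 and power of 80% are therefore not those of this rule. A one-sided arcsine approximation gives n=17.4, rounded up to 18, with power 81.2% at 18. So 18 can be recovered, but the cut-off of 3 does not carry the stated properties.

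**Step 2: the totals.**
- As stated: 4+6+18 = 28 and 4+12+18 = 34. Run-in and Expansion are added, which puts 6+18 = 24 subjects at the MTD.
- If the 6 count within the 18, only 12 more are needed: 4+6+12 = 22 and 4+12+12 = 28, with 18 at the MTD.
- If all combination dose levels are pooled under the stated totals: 6+18 = 24 to 12+18 = 30.

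The sentence in Section 5.1 and the totals cannot both stand. Fewer than 18 is also possible, because 18 is an upper limit and the PPS can drop subjects.

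**Step 3: the rule at each n** (exact alpha at 5% / power at 25%).

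| n | How it arises | Cut-off 3 | Cut-off 4 |
|---|---|---|---|
| 18 | run-in MTD subjects count | 5.8% / 86.5% | 1.1% / 69.4% |
| 19 | 18 + 1 replaced (assumed) | 6.7% / 88.9% | 1.3% / 73.7% |
| 20 | 18 + 2 (assumed) | 7.5% / 90.9% | 1.6% / 77.5% |
| 22 | 18 + 4 (assumed) | 9.5% / 93.9% | 2.2% / 83.8% |
| 24 | 6 + 18 pooled, none replaced | 11.6% / 96.0% | 3.0% / 88.5% |

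At n=30 (all dose levels), cut-off 3 gives 18.8% / 98.9%. Three responses are 16.7% of 18 (exact 95% CI 3.6-41.4%) but 12.5% of 24 (2.7-32.4%).

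**Step 4: replacement and the analysis set.** Under the FAS, replaced subjects stay and the rate is unbiased, but each one adds to n. Under the PPS, a dosed subject who leaves without a follow-up intracranial assessment drops out. The first scheduled scan is at Week 8, so an early withdrawal or adverse-event exit can be unscanned; subjects who progress should have a disease assessment (Section 9.4, Appendix D). If m unscanned non-responders are dropped and 18 are analysed, the apparent rate is p(18+m)/18:
- m=1 (assumed): 0.25 x 19/18 = 26.4%; 5% appears as 5.28%, alpha 6.6%.
- m=2 (assumed): 0.25 x 20/18 = 27.8%; 5% appears as 5.56%, alpha 7.5%.

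**The case against.** The sponsor can say that every statement of the decision rule gives 18, that Section 5.1 expressly carries run-in subjects at the MTD into the Expansion count, and that no passage describes a primary analysis of 24. On that view the totals are merely loose. Section 11.3.2.1 plans percentages with confidence intervals and no test, in a Phase 1 study. Replacing subjects who are not evaluable for DLT is ordinary practice, and the triggers in Section 6.3.2 look like DLT-evaluability criteria.

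Much of this stands. The figure of 24 is inferred by adding up the plan's numbers. A run-in-only reading of Section 6.3.2 is possible, and its effect is small at plausible counts. But if 18 is right, the totals given in the Synopsis and in Sections 5.1 and 5.2 are wrong by 6, a third of the primary sample, and the word additional is wrong too. The absence of a formal test does not remove the go rule in Section 11.1, which needs a fixed n and a named set.

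**Conclusion.** The point holds as an inconsistency and an omission that should be corrected. The current text supports 18 or 24 subjects at the MTD, and no set is named for the primary rate. If the cut-off of 3 is kept, the chance of a go signal at a true 5% rate is 5.8% at n=18 and 11.6%, about double, at n=24. That comparison needs no assumption about replacement. Power rises as well, from 86.5% to 96.0%, so what is lost is control of false go signals.

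Replacement is secondary. An assumed 1-4 replacements kept in the FAS give alpha of 6.7-9.5%. One or two unscanned non-responders dropped under the PPS make a true 25% look like 26.4% or 27.8%.

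Two stronger readings are not supported. A reader might infer that Section 6.3.2 swaps early failures for fresh subjects and so inflates the primary rate substantially; but neither defined set excludes anyone for having been replaced, and progressors should be assessed. A reader might also infer that the trial plans a primary analysis of 24; the documents nowhere say so.

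All figures assume that the 5% null applies to all dosed subjects. Section 11.1 does not give the denominator of the historical rate.

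**What to change.** 1. **Synopsis, 5.1 and 5.2.** Reconcile the Expansion wording with the totals and state the primary n. Either MTD run-in subjects count (n=18, delete the word additional, base totals 22-28), or the 18 are additional and pooled with the 6 (n=24, delete the sentence counting run-in subjects towards Expansion, base totals 28-34). State that the totals exclude replacements.
2. **11.2 and 11.3.2.1.** Define the primary set as all dosed subjects whose assigned starting dose level is the combination MTD, including any replaced for DLT evaluability. Using the assigned starting level keeps out subjects reduced to that level from a higher one. Count a subject with no post-baseline intracranial assessment as a non-responder, and show the PPS as supportive.
3. **6.3.2.** State that replacement of dosed subjects serves DLT/MTD evaluability and removes no one from the efficacy analysis.
4. **11.1.** Tie the cut-off in advance to the final number in the primary set by the exact binomial, and state its exact alpha and power. For n=18 with cut-off 3, restate these as 5.8% and 86.5%. For n=21 to 28, cut-off 4 keeps alpha at or below 5% with power of at least 80% (n=24: 3.0% and 88.5%). At n=18 to 20 neither cut-off meets both limits, so say which property is accepted.

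The cost is wording only. The observed rate may be slightly lower, because unscanned subjects count as non-responders, and one more response is needed wherever cut-off 4 applies.

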#### 7. TREATMENT OF SUBJECTS

#### 7.1. **Description of Treatment Plan**

#### 7.1.1. **Treatment Duration**

Treatment will continue until confirmation of disease progression, unacceptable toxicity, or subject decision to discontinue therapy.

#### 7.2. **Concomitant Medications**

#### 7.2.1. **Permitted Medications**

All medications and other treatments taken by subjects 4 weeks before and throughout the study period will be recorded in the CRF module. Any changes in documented, permitted concomitant medications being taken at the beginning of the clinical trial or added during the time the subject is participating in this study (through the End of Treatment Visit) must be recorded in the CRF module.

#### 7.2.2. **Prohibited Medications**

Concurrent anti-tumor therapy of any kind or any other investigational agent is prohibited. Follow dabrafenib (TAFINLAR) U.S. Product Label recommendations for management of concomitant medications that may cause drug interactions.

#### 7.3. **Treatment Compliance**

E6201 will be administered by IV infusion in clinic by the clinic staff and dose recorded.

Dabrafenib (TAFINLAR) will be supplied by prescription to the subject by the investigator or trained designee for the subject to take on an outpatient basis between visits. Subjects will be supplied with a Patient Diary to record their daily dabrafenib treatment and any missed doses. The Diary will be reviewed by the clinic staff at each patient visit to assess treatment compliance.

#### 7.4. Randomization and Blinding

Not applicable. This study is a non-randomized, sequential-arm study.

Confidential 42 December 31, 2019 Protocol Amendment 4

#### 8. STUDY DRUG MATERIALS AND MANAGEMENT

#### 8.1. E6201

#### 8.2. Study Drug Description

E6201 for Injection is a natural product analog and inhibitor of mitogen-activated protein kinase/extracellular-signal regulated kinase kinase-1 (MEK1). It is a sterile white lyophilized powder containing 60 mg of E6201 formulated in cyclodextrin to improve E6201 solubility in water. See Table 8 for a description of the drug product. The final study drug product will be administered at 320 mg/m² in a total volume of 250 mL intravenously over a 2-hour period twice weekly.

**Table 8: E6201 Investigational Product** 

	Investigational Product				
Product Name:	E6201				
Dosage Form:	E6201 is a lyophilized powder reconstituted in water followed by final dilution into 250 mL normal saline				
Unit Dose	320 mg/m 				
Route of Administration	Intravenous				
Physical Description	White lyophilized powder				
Manufacturer	Eisai, Inc.				

## 8.3. Study Drug Packaging and Labeling

E6201 is packaged in a 20-mL Type I glass vial with a bromobutyl rubber stopper and an aluminum cap for intravenous administration. The study drug vials will be labeled with strength and other information as per local regulatory requirements.

## 8.4. Study Drug Storage

E6201 is demonstrated to be stable when stored in the defined container closure system. E6201 should be stored at 2-8°C and protected from light. Reconstituted and diluted E6201 solutions should be stored refrigerated (2 to 8°C) and protected from light before administration.

## 8.5. Study Drug Preparation

E6201 will be provided directly from the Spirita Oncology drug distribution center.

Each vial contains 60 mg of E6201 and will be reconstituted with 8.5 mL Sterile Water to provide a solution of 10 mL at a concentration of 6.0 mg/mL and pH of 4.5. Once the Sterile Water is added, gently swirl to mix and let sit until totally dissolved. This may take up to 30 minutes to go into solution. Each reconstituted vial will contain 10 mL of E6201 solution. After reconstitution, the appropriate number of vials may be combined as needed per dose calculation. The resulting

Confidential 43
December 31, 2019 Protocol Amendment 4

solution will be diluted to 250 mL in 0.9% Sodium Chloride. Reconstituted and diluted E6201 solutions can be stored at 2-8 °C and for up to 24 hours.

